### **Subgroup analysis**

Subgroup analysis will be based on the ITT dataset per age ( $<65$  years or  $\geq 65$  years old), body mass index ( $<$  or  $\geq 25$ ), smoker or not, alcoholism or not, Charlson comorbidity score ( $<2$  or  $\geq 2$ ), preoperative MMSE score ( $<24$  or  $\geq 24$ ), diagnosis of the surgical lesion (benign vs. malignant), ASA physical status classification (I-II or III), baseline systolic blood pressure ( $<130$  or  $\geq 130$  mmHg), propofol dose used for anesthesia maintenance (divided by the median value), and anesthesia time (divided by the median value).

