## **5. Randomization and blinding**

### **5.1 Randomization**

- 1) A biostatistician who does not participate in data management and statistical analysis will generate random numbers in a 1:1 ratio;
- 2) The results of randomization will be sealed in sequentially numbered envelopes, stored at the site of investigation, and managed by the study coordinator.
- 3) Timing of randomization of individual patient: 30-60 mins before surgery

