### **6.4 Anesthetic care guided by EEG monitoring**

- 1) The monitor screen in the control arm is covered and blinded to the anesthesiologist;
- 2) The monitor in the intervention arm is used by the anesthesiologist to adjust the anesthetic care.
- 3) The goal in the intervention arm is to maintain SEF 10-15 throughout surgery. Avoid burst-suppression.
- 4) In the intervention arm, the anesthesia induction is achieved via propofol pump infusion (slow and controlled). The goal is to avoid burst-suppression and maintain SEF > 10 throughout anesthesia induction.
- 5) The anesthesia maintenance is achieved via the protocol detailed below (6.5). The SedLine-guided intervention protocol is detailed in the **Supplemental remark 1. SedLine-Guided Intervention Flow Chart**.

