### **6.5 Anesthesia protocol for both intervention and control group**

- 1) During the study period (from preop to postop day 5), anticholinergics such as scopolamine are strictly prohibited; atropine or glycopyrrolate can only be used for treatment of bradycardia; the use of midazolam for anxiolysis is allowed but not encouraged;
- 2) In both arms, the anesthesia induction is per standard care using agents of lidocaine, propofol, sufentanyl and muscle relaxant. The administration of propofol in the intervention arm is via pump infusion and guided by SedLine.
- 3) The anesthesia is maintained using propofol infusion (0-200 mcg/kg/min) and remifentanyl infusion (0.05-0.2 mcg/min/kg). Sufentanyl and muscle relaxant boluses can be used during surgery.
- 4) The anesthetic adjustment in the control arm is per the conventional practice (EEG monitored but blinded to anesthesia team) and in the intervention arm per the **Supplemental remark 1. SedLine-Guided Intervention Flow Chart**.

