## 7.2 Intraoperative data

- 1) Surgical details including type and time of surgery;
- 2) Anesthetic details including the name and dose of any drugs used during surgery;
- 3) The total dose of propofol used for anesthesia induction and maintenance;
- 4) Inputs and outputs including the name and volume of the fluid being administered, the estimated blood loss, the urine output, and any blood products being transfused;
- 5) EEG data including the occurrence, duration and percentage of burst-suppression, SEF and PSI (specific to SedLine monitor).

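### Two planned subgroup factors, maintenance propofol dose and (more weakly) anaesthesia time, arise after randomisation and can be changed by allocation, so the comparisons within those halves are not randomised

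*Combined protocol and SAP*

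**What the plan says.** The Subgroup analysis paragraph of section 13.5 lists eleven factors, to be examined in the ITT dataset. Nine describe the patient or the disease: age, BMI, smoking, alcoholism, Charlson score, MMSE, nature of the lesion, ASA class and systolic pressure. The other two are "propofol dose used for anesthesia maintenance (divided by the median value), and anesthesia time (divided by the median value". The paragraph does not set these two apart as post-randomisation, exploratory or non-causal. It does not say whether the median is pooled or taken within arm, or whether dose is a total or a rate per kg. Section 7.2 collects "The total dose of propofol used for anesthesia induction and maintenance". The paragraph also names no interaction test.

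Other sections fix the order of events and the content of allocation:

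- Section 5.1: "Timing of randomization of individual patient: 30-60 mins before surgery".
- Section 6.4: "The monitor in the intervention arm is used by the anesthesiologist to adjust the anesthetic care", and "The goal in the intervention arm is to maintain SEF 10-15 throughout surgery".
- Section 6.4, on induction: "In the intervention arm, the anesthesia induction is achieved via propofol pump infusion (slow and controlled".
- Section 6.5, for both arms: "The anesthesia is maintained using propofol infusion". For usual care: "The anesthetic adjustment in the control arm is per the conventional practice".

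The intraoperative CRF page measures anaesthesia duration from induction to extubation.

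**The concern.** A subgroup comparison keeps the protection of randomisation only if the subgroup would have been the same whichever arm the patient had drawn. Maintenance propofol dose fails that test. Propofol is a maintenance drug in both arms, and the arms differ in what guides its adjustment, so dose is partly a product of the intervention. A patient who would sit in the high-dose half under usual care may sit in the low-dose half under EEG guidance. If the dose a patient needs is also related to delirium risk, the arms inside each half differ in underlying risk.

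Analysing the ITT dataset does not repair this, because the splitting variable is itself affected by treatment. Anaesthesia time is open to the same objection through the arm-specific induction and through emergence. Most of it is presumably operating time, which should make the effect smaller.

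A relative risk by propofol dose invites a mechanistic reading: that guidance works, or fails, in patients given a certain amount of drug. That reading would not be supported, and a larger trial would only narrow the interval around the wrong value.

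**Working it through.** **The plan's own figure.** Section 4.2 assumes 14% delirium, a one-third reduction (to 9.33%), two-sided 5% and 80% power. With the pooled-variance formula and mean risk 0.1167:

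n = [1.960·√(2·0.1167·0.8833) + 0.8416·√(0.14·0.86 + 0.0933·0.9067)]² / 0.0467² = 742 per arm.

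This matches the plan. The present point does not depend on it, but 14% and 742 are the only design inputs the documents supply for what follows.

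**Model (all assumed).** The true effect is null.

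- Vulnerability V is standard normal, and delirium depends on V only, 14% overall.
- Dose = −r·V + √(1−r²)·e − shift·arm, in SD units, where e is standard normal noise and arm is 1 for EEG guidance and 0 for usual care. A positive r means that vulnerable patients need less drug.
- Patients are split at the pooled median.

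**Central case: OR 2.0 per SD of V, r = 0.5, shift = 0.5.** The pooled median lies 0.25 SD below the usual-care mean and 0.25 SD above the EEG mean.

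1. Numbers in the low half: EEG 742·Φ(0.25) = 742·0.5987 = 444; usual care 742·Φ(−0.25) = 742·0.4013 = 298.
2. Mean vulnerability in the low half: EEG 0.5·(0.3867/0.5987) = 0.32; usual care 0.5·(0.3867/0.4013) = 0.48.
3. Mean vulnerability in the high half, by symmetry: EEG −0.48; usual care −0.32. In both halves the EEG patients are 0.16 SD less vulnerable.
4. Delirium risk, by integrating the logistic model over V:

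| Half | EEG | Usual care | Apparent RR |
|---|---|---|---|
| Low dose | 16.5% (n = 444) | 17.9% (n = 298) | 0.92 |
| High dose | 10.3% (n = 298) | 11.4% (n = 444) | 0.91 |
| All | 14.0% | 14.0% | 1.00 |

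Both halves show a benefit that the whole trial does not. With r = −0.5 the halves give 1.10 and 1.09.

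**Range.** With OR 1.5 to 2.0, r 0.3 to 0.5 and shift 0.25 to 0.75 SD, the apparent RR runs from 0.98 to 0.86. With r negative it runs from 1.02 to 1.16. With r = 0 or shift = 0 there is no bias. A 0.1 SD shift, as might apply to anaesthesia time, gives 0.98 to 1.02.

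**Different medians.** In this constant-shift model, arm-specific medians remove the bias. They are not a general cure. If r is 0.3 under usual care and 0.5 under guidance (OR 2.0), arm-specific medians give 1.08 (low) and 0.90 (high). A pooled median with a 0.5 SD shift then gives 1.01 and 0.83. Either way a difference between halves appears although there is no effect anywhere.

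**Precision.** With 371 per arm per half and 14% risk, SE(log RR) = √(2·0.86/(371·0.14)) = 0.182. The 95% CI around RR 1.00 is exp(±1.96·0.182), about 0.70 to 1.43.

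**False positives.** In 20,000 simulated central-case trials, a two-sided 5% test rejects in about 8% (low half) and 7% (high half). At least one half is significant in about 15%, against about 10% without bias.

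**The case against.** The strongest reply is that little hangs on these rows.

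- The plan sets no test or significance rule for subgroups, so the false-positive rates describe an analysis it does not promise.
- In the constant-shift model both halves move together. The ratio of the two RRs is about 0.985, and an interaction test rejects in about 5% of null trials. A reader would see both halves departing from the overall estimate.
- The bias is small beside the sampling error.
- The dose shift is assumed. The flow chart that governs adjustment in the EEG arm is not shown in the text available, so neither its size nor its direction can be read.
- If dose means the total given, duration and body weight will drive much of it, and the standardised shift could be smaller than assumed. This is the same argument that makes anaesthesia time the weaker case.

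Most of this stands as a limit on size. It does not answer the point of principle. Within-half relative risks will be read as treatment effects whether or not a test is attached. The interaction is protected only while the dose–risk relation is the same in both arms, and guidance that responds to each patient's EEG could plausibly change that relation.

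**Conclusion.** The concern holds. Both factors arise after randomisation. For propofol dose, the protocol's own description of the two arms shows that allocation can determine the value; for anaesthesia time the case is the same in principle and weaker in degree. Comparisons inside those halves are not randomised, and nothing elsewhere in the plan corrects this.

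Confidence is high on the principle and low on the magnitude. An apparent RR of 0.86 to 1.16 under a true null rests on an assumed dose shift, an assumed dose–vulnerability correlation and a pooled median, and bias needs both the shift and the correlation. The effect of anaesthesia time has not been measured; 0.98 to 1.02 corresponds to a nominal 0.1 SD shift. The primary comparison, its alpha and the sample size are untouched. Two of the eleven subgroup factors are affected. This should be corrected, but it does not threaten the main result.

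**What to change.** Remove the two factors from the treatment-effect subgroups in section 13.5 and add wording such as:

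> Treatment-effect subgroups use only characteristics fixed before randomisation. Maintenance propofol dose and anaesthesia time will be summarised by arm as process measures. Any analysis relating them to delirium is exploratory and non-randomised (or a mediation analysis with stated assumptions) and will be labelled so.

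State also whether propofol dose is summarised as a total or as a rate per kg. Switching to arm-specific medians is not an adequate substitute.

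If a stand-in for duration is wanted, planned procedure type could serve, provided it is taken from the preoperative schedule. Section 7.2 and the CRF record the type or name of surgery with the intraoperative data, so the source needs to be specified.

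The cost is SAP wording and the loss of two exploratory subgroup rows. Dose and duration are already collected (section 7.2 and the intraoperative CRF page), and the conduct of anaesthesia does not change.

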## **14. Quality control and quality assurance**

### **14.1 For investigators/care givers**

- 1) Trial protocol will be thoroughly explained to all investigators/care givers before the start of the trial. The trial protocol must be strictly adhered throughout the trial period;
- 2) All expected and unexpected findings will be documented promptly and correctly in order to guarantee the reliability of the values;

- 3) The monitors and instruments that are used during the study period will be checked and corrected regularly in order to guarantee their normal function;
- 4) Data analysis will be performed by the statisticians and investigators;
- 5) Any conclusions must be derived from the original data.

#### **14.2 For participants**

- 1) Possible benefits and risks associated with the study will be clearly explained to every potential participant;
- 2) Written informed consent must be signed by every enrolled patient, or by the authorized surrogate of the patient;
- 3) If the enrolled patients refuse to participate in the study during the study period, the patient will be excluded for further study.

#### **14.3 Study termination**

- 1) If a study-related death occurs during the study period, the study will be stopped. A report will be sent to the Ethics Committee. Restart of the study will need an approval from the Ethics Committee;
- 2) The study will be terminated after accomplishment of patient recruitment and data collection. Decision will be made by the principal investigator.

#### **15. Ethics requirement and written informed consent**

- 1) Helsinki declaration and Chinese guidelines of Good Clinical Practice will be strictly followed. The study protocol must be approved by the Ethics Committee before the study can be started;
- 2) For every potential participant, investigators have the responsibilities to fully explain the study purpose, procedures, as well as possible risks in a written informed manner. They must let every potential participant know that he/she has the right to withdraw his/her consent at any time during the study period. Every potential participant must be given a written informed consent. Every participant or the authorized surrogate of the patient must sign the consent before they can be enrolled in the study. Written informed consents will be kept as a part of the clinical trial documents.

#### **16. Preservation of documents**

Investigators will carefully preserve all documents and data of the clinical trial according to the Good Clinical Practice requirement.

#### **17. Declaration of interests**

None declared.

#### **18. References**

Included under each section, respectively.

## **Section C: Neurocognitive and Delirium Assessment**

**See Supplemental Remarks 2-4**

## Section D: Definitions of Postoperative Complications

Complications	Definition
Circulatory insufficiency	Requirement of inotropic agents or vasopressors after surgery
Acute myocardial ischemia or infarction	Concentration of cardiac troponin I exceed the diagnostic criteria for myocardial ischemia or infarction as well as new Q waves (lasts for 0.03 s) or continuous (4 days) abnormal ST-T segment
Arrhythmia	Confirmed by 12-lead electrocardiogram and necessitated medical treatment and/or cardioversion
Pulmonary infection	New infiltrate on chest radiograph combined with temperature over 38°C and leukocytosis
Acute respiratory failure	Severe hypoxemia or hypercapnia requiring endotracheal intubation and mechanically assisted ventilation
Stroke	Persisted new focal neurologic deficit and confirmed by neurologic imaging
Acute kidney injury	Creatinine elevation meeting the current diagnostic criteria
Wound infection or dehiscence	Wound infection (purulent discharge or positive bacterial culture) or rupture that required secondary suturing
Ileus	Abdominal distention, bloating, and "gassiness", Diffuse, persistent abdominal pain, Nausea and/or vomiting, Delayed passage of or inability to pass flatus, or Inability to tolerate an oral diet, for more than 3-5 days
Anastomotic leakage	Extravasation of contrast agent in the body cavity or retroperitoneal space that required percutaneous drainage
Severe sepsis	Two or more criteria of systemic inflammatory response syndrome, with known infection and new onset dysfunction of at least one system
Urinary tract infection	Confirmed by urinalysis and urine culture and necessitated antibiotic therapy

## Illustration

1. This is a prospective, randomized controlled study. All recorded data must be timely, accurate and complete.
2. If error(s) occurs in filling data, please use ONE strikethrough line and refill the correct data, and sign name of the corrector and date of correction. Attention: Do not cover the original data; do not use the eraser or correction fluid; do not cross more than one strikethrough line.
3. Every page and every item of the case report form (CRF) must be completed. Fill “√” in the “□” to indicate selection; “UK” to indicate “do not know” or “unknown”, “NA” to indicate “cannot provide” or “not applicable”.
4. Patient’s abbreviated name (initials of the last and first name) will be recorded in the form of left aligned acronym of Chinese phonetic alphabet. For example:  
Zhang Wei will be recorded as: ZW;  
Zhang Xiao-Wei will be recorded as: ZXW;  
Ou-Yang Xiao-Wei will be recorded as: OYXW.  
For studies in the USA, the initial of the first name is placed before the initial of the last name. For example:  
John Webber will be recorded as: JW (John is the first name).
5. The number of recruited patients will be recorded in four numbers. For example:  
No. 1 will be recorded as: 0001;  
No. 12 will be recorded as: 0012;  
NO. 123 will be recorded as: 0123;  
NO. 1234 will be recorded as: 1234.
6. Numeric data such as body weight and height will be recorded with one decimal, for example:  
Body weight 65 kg will be recorded as: 65.0 kg;  
Height 165.5 cm will be recorded as: 165.5 cm.
7. Date will be recorded as year-month-day, for example:  
January 1st of 2016 will be recorded as: 2016-01-01;  
December 16th of 2016 will be recorded as: 2016-12-16.
8. Duration of education is the actual years of education.
9. The time will be recorded in the form of hh:mm, and use a 24-hour clock. For example:  
9:35 in the morning will be recorded as: 09:35;  
2:05 in the afternoon will be recorded as: 14:05.
10. If investigators have any questions during the study period, please contact the principle investigator ([name] or [name]). In case of severe adverse events which must be recorded, responsible investigator must report to the supervising authorities including the principal investigators and the Ethics Committees within 24 hours.

## Flow chart of the study

	Screen	Recruitment	Intraoperative	Postoperative follow-up								
				PACU	D1	D2	D3	D4	D5	D6-discharge	D30±3	
Inclusion/exclusion criteria	X	X										
Informed consent	X											
Demographic data	X	X										
Preoperative diagnosis	X	X										
Previous medical history	X	X										
Physical examination	X	X										
Auxiliary examination	X	X										
MMSE	X	X										
Baseline CAM	X	X										
Anesthesia			X									
Study protocol execution		X	X	X	X	X	X	X	X	X	X	X
Delirium assessment*				X	X	X	X	X	X			
Adverse events				X	X	X	X	X	X	X		
NRS of severity of pain				X	X							
NRS of subjective sleep quality					X							
Use of other drugs				X	X	X	X	X	X	X		
Postoperative complications**				X	X	X	X	X	X	X		X
All-cause 30-day mortality												X

\*Delirium will be assessed at PACU and twice daily (8:00-10:00 am and 18:00-20:00 pm) during postoperative day 1 to 5.

\*\*Patients will be followed up until postoperative day 30.

**Inclusion Criteria:**

Age $\geq$ 50 years	Y 	N 
ASA physical score I-III	Y 	N 
Scheduled to undergo elective laparoscopic surgery under general anesthesia with endotracheal intubation	Y 	N 
Able to undergo MMSE and CAM assessment	Y 	N 
Extubation expected after surgery	Y 	N 
Scheduled to stay in hospital > 3 days after surgery	Y 	N 

\*Subjects cannot be enrolled in the study if any one of the above is "N"

**Exclusion Criteria:**

Refuse to participate	Y 	N 
Emergent surgery or trauma patients	Y 	N 
Preoperative cognitive impairment characterized by MMSE of 23 or less	Y 	N 
Preoperative history of stroke, TIA, schizophrenia, Parkinson's disease, epilepsy, or dementia	Y 	N 
Inability to communicate in the preoperative period due to language difficulties, or significant hearing or visual impairment	Y 	N 
Severe cardiac disease including low-output cardiac failure defined as a preoperative left ventricular ejection fraction < 30% or arrhythmia with pacemaker or AICD placement	Y 	N 
Severe hepatic dysfunction being evaluated for liver transplantation or with a Child-Pugh Class C classification	Y 	N 
Severe renal dysfunction requiring renal replacement therapy before surgery	Y 	N 
Those with preoperative ASA classification of 4 or who are unlikely to survive for more than 24 hours after surgery	Y 	N 

\*Subjects cannot be enrolled if anyone of the above is "Y"

Preoperative comorbidity	Cognitive function	MMSE Score: ____;  Dementia		
	Neuropsychiatric diagnosis	 None;  Stroke;  TIA;  Schizophrenia;  Parkinson's disease;  Epilepsy;  Depression		
	Cardiovascular system	 None;  CAD;  VHD;  Congenital heart disease;  Hypertension;  Arrhythmia;  Cardiomyopathy;  Others: _____		
		 Current NYHA classification: ____  I: No symptoms and no limitation in ordinary physical activity, e.g. no shortness of breath when walking, climbing stairs etc.  II: Mild symptoms (mild shortness of breath and/or angina) and slight limitation during ordinary activity.  III: Marked limitation in activity due to symptoms, even during less-than-ordinary activity, e.g. walking short distances (20–100 m). Comfortable only at rest.  IV: Severe limitations. Experiences symptoms even at rest. Mostly bedbound patients.		
	Respiratory system	 None;  COPD;  Chronic bronchitis;  Asthma;  Smoke (>10 cigarettes/d, > 1 year), ____ packs/d, ____ years  Others: _____		
	Metabolic disorders	 None;  Diabetes;  Thyroid disease;  Hyperlipidemia;  Hepatic dysfunction (ALT and/or AST $\geq$ 5 times of upper limit);  Renal dysfunction (Cr $\geq$ 177 $\mu$ mol/L);  Electrolyte disorder;  Morbid obesity; BMI ____  Others: _____		
Others	 Alcoholism* ____ ml/day; ____ years  GI disorders;  AIDS;  Cancer  History of allergy: _____  Others: _____			
History of surgery	 No			
	 Yes	Date	Surgery	Anesthesia

\*Two drinks or more daily, or weekly consumption of the equivalent of 150 ml of alcohol.

Updated Charlson Comorbidity Index Score = \_\_\_\_\_

Comorbidity	Charlson weight score	Score of the patient
Myocardial infarction	0	
Congestive heart failure	2	
Peripheral vascular disease	0	
Cerebral vascular disease	0	
Dementia	2	
Chronic lung disease	1	
Rheumatic diseases	1	
Ulcer of digestive tract	0	
Mild liver disease	2	
Diabetes without chronic complications	0	
Diabetes with chronic complications	1	
Hemiplegia or paraplegia	2	
Renal disease	1	
Malignant tumor (including leukemia and lymphoma)	2	
Moderate / severe liver disease	4	
Metastasis of solid tumors	6	
AIDS/HIV	4	
Total score	24	

**Preoperative drugs**

Use of sedatives & analgesics during the night before surgery:  No;  Yes			
Check if yes	Drug	Dose	Route
			
			
			
Premedications:  No;  Yes			
Check if yes	Drug	Dose	Route
	Scopolamine		
	Atropine		
	Glycopyrrolate		
	Midazolam		
	Other:		
	Other:		
	Other:		

